3.1.2 Food Introduction

If research subjects have a clinical response to dupilumab, they will introduce an EoE trigger food at one serving size per day. After 12 weeks, repeat EGD and symptoms score will be obtained. 12 weeks is being used as determined clinical and histologic responses can be seen at that time point in previous clinical studies¹⁸.

The foods (milk, egg, soy, and wheat) to be introduced after having caused exacerbation of their EoE by standard definitions:

- Addition of a single food lead to exacerbation of esophageal eosinophilia (increase of greater than 15 eos/hpf) or
- Removal of a single food lead to normalization of biopsy (esophageal eosinophilia showed less than 6 eos/hpf)
- AND
- History of either milk, egg, soy, or wheat induced EoE based on introduction of the food and symptoms in the last 12 months

Foods in phase 1 will be introduced as one serving size at week 13. If biopsy at week 25 are less than 6 eosinophils/HPF, the subjects will have one of 2 options

- Increase the serving size to 2 servings a day or
- Add an additional EoE trigger food

If the week 25 biopsy show 6-15 eosinophils/hpf, the diet will remain the same

If the week 25 biopsy show >15 eosinophils, the diet will decrease to ½ serving size a day

For the week 38 endoscopy with biopsy, the three scenarios are

If the biopsy show < 6 eosinophils/hpf, the three options are

- Increase the serving size to ad lib (if one food) or
- Add a 3rd EoE trigger food or
- Increase the serving size of 1st and 2nd foods to 2 serving size a day

If the biopsy shows 6-15 eosinophils/hpf, the plan is to remain at the current diet

If the biopsy show >15 eosinophils/hpf, the plan is to decrease the serving size by 50%

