6. Narrow caliber esophagus defined as the inability to pass a 9.5 mm endoscopy into the esophagus
7. IgE mediated reaction to food (milk, egg, soy, or wheat) being introduced in the last 12 months
8. No change in the dose of swallowed steroids for Eosinophilic Esophagitis for 2 months prior to starting the study and throughout the study (their current standard of care EoE treatments)

Number Of Subjects 30 patients

Study Duration Each subject's participation will last 52 weeks

Study Phases 1) The first phase is the initial disease control in patients with

Disease Control Eosinophilic Esophagitis. Subjects will be treated with dupilumab for 12 weeks (per current proposed dosing in EoE clinical trials)

Food introduction

-
- a. At the end of the 12 weeks, subjects will have endoscopy showing resolution of EoE
- 2) **Food introduction:** If subjects do not have active esophageal biopsies (defined by greater than 15 eos/hpf) and have decreased symptoms per EoE symptom score, the subjects will continue dupilumab at current dosing regimen
- a. They will introduce one food (per food introduction guideline) for 12 weeks, then, upper endoscopy with biopsy will be done to examine EoE disease status
 - b. If biopsies are normal, second food can be added, final endoscopy will be performed at week 51 to determine the stability of food introduction on dupilumab
 - i. If a 3rd food was shown to be causative, it can be added at week 38.

Efficacy Evaluations	Esophageal Biopsy (Eosinophils/high power field) Esophageal Symptom Scores
Pharmacokinetic Evaluations	Not applicable
Safety Evaluations	Safety measures including symptom score, adverse events from dupilumab and endoscopies will be collected at each visit.
Statistical And Analytic Plan	
The primary statistical efficacy endpoint will be tested using a Paired T-test on the change in peak eosinophil counts on esophageal biopsies between 1st and 2nd endoscopy after food introduction in the same patient.
 
If peak eosinophil counts do not satisfy the assumption of normality, instead the Wilcoxon Signed-Rank test will be used for the primary.

DATA AND SAFETY MONITORING PLAN	The principal investigator will be responsible for the safety and monitoring of the study and data validation of the study.

TABLE 1: SCHEDULE OF STUDY PROCEDURES

Study Phase	Disease Control				Food introduction												Follow-up
	1	2	3	4	5	6*	7*	8	9	10*	11*	12	13	14*	15*	16	17

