3 INVESTIGATIONAL PLAN

3.1 General Schema of Study Design

This study is an open label exploratory study to examine if patients controlled with dupilumab can successfully introduce EoE trigger foods back into their diet.

In the initial 12-week period, patients will start on dupilumab on the doses used in the phase 3 trials to control disease. If disease is controlled based on histologic and symptom control at week 12 endoscopy, patients will start on EoE trigger food. The trigger foods will be based on both a combination of history and histology results. The food will have triggered EoE by histology in the last 2 years and symptoms in the last year when reintroduced into the diet. The study will focus on the four most common foods that trigger EoE: milk, egg, wheat, and soy. For the initial food introduction, the subjects will add one serving size of the food daily for 12 weeks. After 12 weeks, the subjects will have a 2nd endoscopy if the 2nd endoscopy is normal, the subjects will increase the trigger food to 2 serving sizes a day or add an additional trigger food. A 3rd endoscopy will be done if the patients increase the food amount or adds a new food at week 38 (12 weeks after adding the new food). If the subject does not increase or add new foods at week 25, the 3rd endoscopy will not be obtained. All subjects will have end of study endoscopy at week 51.

If the subjects have abnormal endoscopy or increase in symptoms, the amount of food will be reduced by 50% and repeat endoscopy will be obtained at the same time schedule-12 weeks later. (See Figure 1 and Table 1)

Screening Phase

Potential subjects will be screened using the protocol inclusion and exclusion criteria based on review of their medical records.

Parental/guardian permission (informed consent) and, if applicable, child assent, will be obtained prior to any study related procedures being performed. After consent is obtained, research blood samples will be drawn to confirm eligibility based on clinical laboratory parameters. Females of child bearing potential will have an urine pregnancy test.

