7.10 Regulatory and Ethical Considerations

7.10.1 Data and Safety Monitoring Plan

The principal investigator (PI) will monitor adverse events and other safety concerns during the study. As the drug is approved for this age group and has been studied in this indication, little new adverse events are expected. The main novel adverse event will be with food introduction while on dupilumab. The symptoms and side effects will be monitored at regular study visits for worsening EoE symptoms. In addition, the endoscopies at week 12 after the introduction will examine if active disease has returned and the food introduction will be adjusted.

The PI will ensure the accuracy, security, and validity of the data via oversight of data storage, integrity, and laboratory methodology including statistical analysis. The PI will provide oversight of study personnel to ensure the safety of enrolled subjects by enforcing the protections and safeguards outlined in the protocol.

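### A subject who flares on one serving at week 25 and remits on half a serving by week 38 has only one listed option that fits: unlimited intake

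*Combined protocol and SAP*

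**What the plan says.** Every subject who enters food introduction starts with one trigger food at one serving a day (section 3.1.2). The ladder then has two decision points.

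**Week 25.** Below 6 eos/hpf, the subject either goes to two servings or adds a second food. At 6-15 the diet is unchanged. Above 15: "If the week 25 biopsy show >15 eosinophils, the diet will decrease to" half a serving a day. The synopsis and section 3.1 also make escalation depend on a normal biopsy: "If biopsies are normal, second food can be added, final endoscopy will be performed at week 51" and "if the 2nd endoscopy is normal, the subjects will increase the trigger food to 2 serving sizes a day", with an additional food as the alternative in 3.1.

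**Week 38.** Below 6 eos/hpf there are three options: "Increase the serving size to ad lib (if one food) or" adding a third trigger food, or "Increase the serving size of 1st and 2nd foods to 2 serving size a day". At 6-15 the diet is held; above 15 it is halved. The Table 1 notes repeat the same list.

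Section 3.1 says two things about the week-38 endoscopy. One sentence reads "If the subject does not increase or add new foods at week 25, the 3rd endoscopy will not be obtained". The next paragraph, on subjects with an abnormal endoscopy or more symptoms, reads "the amount of food will be reduced by 50% and repeat endoscopy will be obtained at the same time schedule-12 weeks later". Table 1 schedules an EGD at week 38.

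Section 7.10.1 describes the safeguard: "the endoscopies at week 12 after the introduction will examine if active disease has returned and the food introduction will be adjusted".

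**The concern.** The week-38 step depends on the week-38 count and the number of foods, and on nothing that happened at week 25. That reverses the logic of the ladder. A subject who tolerated one serving may raise that food only to two servings and must pass another biopsy before intake becomes unlimited. A subject who flared on one serving can go from half a serving straight to unlimited, skipping the dose that failed. A count below 6 on half a serving is not evidence that one serving is now tolerated, still less unlimited intake.

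What is at stake is subject safety, not inference. Section 7.10.2.3 names worsening histology and possible fibrosis as a risk separate from symptoms and relies on a biopsy 12 weeks after the food step to detect it. A step taken after week 38 is next biopsied at week 51, when treatment ends (section 3.3.1), so no food adjustment within the study can follow.

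**Working it through.** The plan gives no figure to reproduce for this rule. The check traces each week-25 outcome to the week-38 options that fit it, then works out timing and possible numbers.

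**Trace (section 3.1.2 and Table 1 notes), assuming week 38 is below 6 eos/hpf**

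| Week-25 result | Diet from week 26 | Listed options that fit |
|---|---|---|
| <6, serving raised | one food, 2 servings | ad lib |
| <6, food added | two foods | third food; both foods to 2 servings |
| 6-15 | one food, 1 serving | ad lib |
| >15 | one food, ½ serving | ad lib only |

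In the last row, a third food and a rise in the first and second foods both need two foods in the diet. This subject has one, because a second is offered only after a normal (<6) week-25 biopsy. No option holds at half a serving or returns to one serving.

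**Is the branch reachable?** Yes, on the more specific text. The paragraph in 3.1 on subjects whose food is cut orders a repeat endoscopy 12 weeks later, and Table 1 has a week-38 EGD. The general sentence in 3.1 can be read as covering subjects whose diet was simply held.

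**Timing (Table 1, section 4.2.1).** Visit 12 (biopsy) is week 38, visit 13 (food change) is week 39, and the next EGD is visit 16, week 51. Interval from the food change: 51 − 39 = 12 weeks; from the last biopsy: 51 − 38 = 13 weeks. Symptom scores are taken at weeks 39, 41 and 46.

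**Possible numbers.** Section 5.6 assumes 64% of 30 subjects reach food introduction: 30 × 0.64 = 19.2, about 19. Let q be the share of these who both exceed 15 eos/hpf at week 25 and fall below 6 on half a serving. The documents give no value for q, so the values here are assumptions.

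- Expected number = 19q.
- P(at least one) = 1 − (1 − q)^19.

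| q (assumed) | Expected number | P(at least one) |
|---|---|---|
| 0 | 0 | 0 |
| 0.01 | 0.19 | 0.174 |
| 0.05 | 0.95 | 0.623 |
| 0.10 | 1.9 | 0.865 |

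Break-even points: P = 0.5 at q = 1 − 0.5^(1/19) = 0.0358; expected number = 1 at q = 1/19 = 0.0526.

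**Primary endpoint (section 5.3.1).** It compares a first and a second endoscopy. Whether those are weeks 12 and 25 or weeks 25 and 38, both precede the week-39 food change. All other testing is exploratory (section 5.5).

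**The case against.** The strongest reply is that the week-38 list was written for subjects who escalated at week 25. Its options match them: one food at two servings goes to ad lib, and two foods go to a third food or to larger servings. On that reading a clean week-25 biopsy is implied. Read literally, the general sentence in 3.1 even denies the reduced subject a week-38 endoscopy, so the list is never reached. Section 3.1 also refers the reader to Figure 1, which is not visible and may show a separate branch.

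Nor is anyone compelled to take the step. The items are options, and ad lib is a permission rather than an assigned dose. The investigator may withdraw a subject (sections 3.4.4 and 4.6), food is cut if symptoms rise (3.1), unscheduled visits are allowed (4.4), and there is telephone follow-up for symptoms (7.10.2.3). Twelve weeks to biopsy is the design interval for every food step, section 7.10.2.2 treats three to four months as routine, and every food introduced is already a known trigger. Finally, q is assumed, and 19 allows for no dropout after week 12.

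Much of this stands. The point is conditional on Figure 1, the number of subjects may be zero, and the interval to the week-51 biopsy is shared with every other week-38 change. Three things remain. The implied condition is not written in either place where the list appears. The paragraph specific to reduced subjects does give them a repeat endoscopy. And none of the symptom-based safeguards would detect a flare without symptoms. If Figure 1 differs, the written rule is still wrong in two places.

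**Conclusion.** The concern holds on the visible text and is minor. For a one-food subject reduced after a week-25 flare who is below 6 eos/hpf at week 38, ad lib is the only listed option that fits. It permits a move from 0.5 serving a day to no limit, on a food that gave more than 15 eos/hpf at 1 serving.

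The conclusion rests on reading the specific repeat-endoscopy paragraph in 3.1 as governing and on Figure 1 not adding a condition; confidence is moderate for those reasons. Over an assumed q of 0% to 10%, between 0 and 1.9 subjects are expected, with a 0% to 86% chance of at least one. What is specific to this branch is the lifted limit, not the monitoring interval.

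**What to change.** 1. In section 3.1.2 and the Table 1 notes, state that ad lib does not apply to subjects reduced after more than 15 eos/hpf at week 25. If they are below 6 at week 38, they stay at half a serving or at most return to one.
2. In section 3.1, reword the sentence on omitting the third endoscopy so that reduced subjects clearly have it at week 38, in line with the following paragraph and Table 1.
3. Align Figure 1 if it differs.

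The cost is a few lines of wording, with no procedure beyond Table 1 and no extra subjects. Escalation would be slower for a few subjects. A return to one serving would also go without a biopsy until week 51, so the gain is a limit and an explicit hold, not closer monitoring.

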3.1.3 Follow-up Phase

The follow-up phase will continue for up to 14 days to monitor for adverse events.

3.2 Allocation to Treatment Groups and Blinding

All patients will receive active drug.

3.3 Study Duration, Enrollment and Number of Sites

3.3.1 Duration of Subject Study Participation

If subjects complete all phases, the study will last 52 weeks. 51 weeks of treatment and 1 week of follow-up. If the subject does not meet study criteria (response to dupilumab), they will exit the study at week 13.

3.3.2 Total Number of Study Sites/Total Number of Subjects Projected

The study will be conducted at approximately 1 investigative site in the United States.

3.4 Study Population

Children, adolescent, and adults with Eosinophilic Esophagitis

3.4.1 Inclusion Criteria

3.4.2 Index/Case Subject Inclusion Criteria

- 1) Males or females age 6 to 25 years
- 2) Diagnosis of Eosinophilic Esophagitis based on the most recent international consensus definition (Dellon et al, Gastroenterology 2019)
 - a) History of endoscopy with a peak count of >15 eosinophils per high powered field meeting consensus criteria for Eosinophilic Esophagitis¹
- 3) History of either milk, egg, soy, or wheat induced EoE based on the following criteria in the last two years
 - a) Addition of a single food lead to exacerbation of esophageal eosinophilia (increase of greater than 15 eos/hpf) or
 - b) Removal of a single food lead to normalization of biopsy (esophageal eosinophilia showed less than 6 eos/hpf)

AND

 - c) History of either milk, egg, soy, or wheat induced EoE based on introduction of the food and symptoms in the last 12 months
- 4) Weight \geq 10 kg
- 5) Ability to remain on stable dose of PPI therapy throughout the study
- 6) Women with child bearing potential must have a negative urine/serum pregnancy test.
- 7) Parental/guardian permission (informed consent) and if appropriate, child assent.

3.4.3 Exclusion Criteria

1. Tracheo-esophageal fistulas, inflammatory bowel disease, Barrett's disease, or other significant inflammatory disease of the gastrointestinal tract
 2. Biopsy evidence of eosinophilic infiltration in any other organ system
-

3. History of significant esophageal procedures e.g., sclerotherapy or esophagectomy
 4. Systemic immunosuppressant usage in prior 3 months and throughout the study
 5. Narrow caliber esophagus defined as the inability to pass a 9.5 mm endoscopy into the esophagus
 6. IgE mediated reaction to food (milk, egg, soy, or wheat) being introduced in the last 12 months
 7. Therapy with biologic molecule (e.g., omalizumab, infliximab) in prior 12 months
 8. Any factors that may pose a significant risk for undergoing anesthesia/sedation
 9. Subjects undergoing any type of immunotherapy to any food (oral immunotherapy, sublingual immunotherapy, specific oral tolerance induction) within 3 months prior to Visit 1.
 10. Active IgE- mediated milk, egg, wheat, or soy allergy based on skin test or history (if those foods are being introduced back into the diet).
 11. Allergy or known hypersensitivity to the dupilumab.
 12. Subjects (or parents of subjects) with obvious excessive anxiety and unlikely to cope with the conditions of an upper Endoscopy and biopsy.
 13. No change in the dose of swallowed steroids for Eosinophilic Esophagitis for 2 months prior to starting the study and throughout the study (their current standard of care EoE treatments
 14. Past or current disease(s), which in the opinion of the Investigator or the Sponsor, may affect the subject's participation in this study, including but not limited to active autoimmune disorders, immunodeficiency, malignancy, uncontrolled diseases (hypertension, psychiatric (especially anxiety), cardiac), or other disorders (e.g., liver, gastrointestinal, kidney, cardiovascular, pulmonary disease, or blood disorders).
 15. Participation in another clinical intervention study in the three months prior to Visit 1.
 16. Subjects unable to follow the protocol and the protocol requirements.
 17. Subjects on any experimental drugs or treatments.
 18. Subjects unable to read/understand English or follow the protocol and the protocol requirements.
 19. Treatment with a live (attenuated) vaccine within 4 weeks before the baseline visit or throughout the trial
 20. Major elective surgeries are prohibited during the study
 21. Female patients who are pregnant, breastfeeding, or planning to become pregnant or breastfeed during the study
 22. Women of children bearing potential (WOCBP) who are unwilling to practice highly effective contraception prior to the initial dose/start of the first treatment, during the study, and for at least 12 weeks after the last dose. This includes female patients who experience menarche during the study duration and who are unwilling to follow the precautions for WOCBP.
-

23. Chronic or acute infection requiring treatment with systemic antibiotic, antivirals, or antifungal within 2 weeks of baseline visits

a. Patients maybe rescreened after infection resolves

24. Participants with active or suspected parasitic infection are excluded.

3.4.4 Individual stopping rules

Subjects may withdraw from the study/schedule of assessments for any of the following reasons:

- Patients will be stopped if they have severe adverse reaction from a serious adverse event from injection reaction
- The Investigator decides that it is the subject's best interest to be withdrawn from the study.
- The subject is unwilling to continue in the study (consent withdrawal).
- Lack of compliance with protocol requirements and procedures.
- The Sponsor- Investigator or Regulatory Authorities, for any reason, stops the study.
- The subject fails to return to the clinic for scheduled visits and does not respond to telephone or written attempts at contact (lost to follow-up).
- Subject's death

The reason for withdrawal will be recorded in the clinical records and the electronic Case Report Form (eCRF). All subjects who are withdrawn or discontinue should be provided with alternative medical care, if applicable.

4 STUDY PROCEDURES

Eosinophilic Esophagitis History

Physical examination

Esophagogastroduodenoscopy with biopsy with conscious sedation:

Eosinophilic Esophagitis Symptom Score:

Pediatric Eosinophilic Esophagitis Symptom Score

Pediatric Eosinophilic Esophagitis Symptom Questionnaire

Eosinophilic Esophagitis Quality of Life Measures

- PedsQL™ Eosinophilic Esophagitis Module Version 3 Teen Report (ages 13-18)
- PedsQL™ Eosinophilic Esophagitis Module Version 3 Child Report (ages 8-12)
- PedsQL™ Eosinophilic Esophagitis Module Version 3 Parent Report for Child (ages 8-12)
- PedsQL™ Eosinophilic Esophagitis Module Version 3 Parent Report for Young Child (ages 5-7)

Esophageal Compliance measured by Endoflip

Research esophageal biopsies-6 additional esophageal biopsies

Blood draws for exploratory markers (RNAseq transcriptome of blood, T cell proliferation, peripheral blood eosinophils and progenitors)-15 ml per blood draw

Diet records

Study Drug administration

4.1 Study Treatment Phase: EoE disease control

4.1.1 Visit 1

Visit 1: Baseline Visit, Study enrollment

- Informed consent obtained,
- Inclusion and exclusion criteria reviewed,
- Medical Records reviews
- Physical exam including vital signs with height and weight
- Eosinophilic Esophagitis Symptom Score-Pediatric Eosinophilic Esophagitis Symptom Score (PEESS and PESQ)
- EoE Quality of life (QOL)
- Research labs (T cell phenotype, PBMC RNAseq, peripheral blood eosinophils and progenitors, proteomics)-15 ml
- First dose of Dupilumab

4.1.2 Visit 2

2 weeks from visit 1 (+/- 3 days)

- EoE Symptom Score-PEESS and PESQ
- Drug disposition
- Monitor drug compliance
- AE assessment
- Physical Examination including vital signs with height and weight

4.1.3 Visit 3

5 weeks from visit 2 (+/- 4 days)

- EoE Symptom Score-PEESS and PESQ
- Drug disposition
- Monitor drug compliance
- AE assessment
- Physical Examination including vital signs with height and weight

4.1.4 Visit 4

4 weeks from visit 3 (+/- 4 days)

- Upper Endoscopy with biopsy with 4 esophageal biopsies for histology
- EoE Symptom Score-PEESS and PESQ
- EoE QOL
- Drug disposition
- Monitor drug compliance

- AE assessment
- Physical Examination including vital signs with height and weight
- Endoflip and/or esophageal impedance
- Research bloods (T cell phenotype, PBMC RNAseq, peripheral blood eosinophils and progenitors, proteomics)-15 ml of blood
- Research Biopsies (esophageal RNAseq)-6 esophageal biopsies for research samples

